### 6.3.3 Deaths

The death form will be completed by the Principal Investigator from the involved Clinical Center, who will classify the death using a modification of the HEMO Study coding system. This system will allow for the classification of deaths by organ system, such as cardiac and infection-related. A death packet with the death form and specific patient information will be sent by the Clinical Center to the Data Coordinating Center, who in turn will forward this data to members of the Outcome Committee. For hospitalizations resulting in death, the same information as described above for hospitalizations will be obtained. If the death did not occur in the hospital, then the principal investigator will provide a narrative describing the circumstances of the patient's death and the presumed cause of death based on the patient's history and events leading up to the patient death. One member of the Outcome Committee will review this information and verify the cause of death on the death form. If the death coded by the Outcome Committee member and the Clinical Center PI differ, then the case will be discussed by the Outcome Committee during the monthly conference call. The death code chosen by the committee will be used for subsequent analysis.

#### 6.3.4 Vascular Access Complications

All vascular accesses will be tracked for complications using a modification of the Dialysis Access Consortium (DAC) Study vascular access forms. A form will be completed on each patient at the time of randomization that will classify the type and location of the vascular access in use at that time. A vascular access complication form will be completed whenever the study patient undergoes one or more of the following vascular access procedures: access failure (thrombosis or removal requiring placement of a new access), placement of a new vascular access, access intervention (angioplasty, stenting, surgical revision, fibrin sheath stripping, etc., but not TPA instillation or venogram only). The procedures performed for these access complications will also be noted on this form. Vascular access infections not requiring removal of the access will not be recorded. Information on vascular access complications will be provided to the DSMB to monitor the rates of access complications in each arm of the study.

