## Safety

3) To determine the safety of the nocturnal hemodialysis intervention, with a particular emphasis on vascular access and patient burden.

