	Feeling Thermometer score
	Medical Outcomes Study Sleep Scale
	Lower Extremity Performance Battery* score
Depression/Burden of Illness	Beck Depression Inventory, v1 score
Cognitive Function	Trailmaking Test B score
	Modified Mini-Mental Status score
Nutrition and Inflammation	Serum albumin
	Normalized protein catabolic rate
	Body mass index
	Lean body mass by single frequency bioimpedance analysis

Mineral Metabolism	Predialysis serum phosphate
	Predialysis serum calcium
	Calcium-phosphate product
	Parathyroid hormone
	Phosphate binder dose
Survival and Hospitalization	Rate of non-access hospitalizations or death
	Rate of access hospitalizations
	Rate of all hospitalizations or death
	Rate of cardiovascular hospitalizations or death
	Total hospital days (over 12 months)
Hypertension	Average pre-dialysis blood pressure
	Average post-dialysis blood pressure
	Average pulse pressure
	Proportion of patients with wkly average predialysis systolic blood pressure <110 mmHg
	Number of prescribed antihypertensives
Anemia	Pre-dialysis hemoglobin
	Erythropoietin dose
	Cumulative intravenous iron requirements (over 12 months)
	Serum ferritin and transferrin saturation
Adverse Events and Risks:	
Vascular Access Complications	Time to first access intervention
	Rate of access interventions
	Time to first access failure
	Rate of access failures
	Rate of infection related failures
Patient Burn-out	Proportion of patients requiring dialysis modality change over 12 months
	Monthly average number of missed treatments (baseline and monthly)
	Weekly average number of shortened treatments (baseline and monthly)
Treatment Burden:	
Patient Burden	Minutes to recovery
	Proportion of patients wishing to continue, or switch to nocturnal HD at 12 months

\*gait speed, time to stand, standing balance

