# 5.1.5.6 Vascular Access Events

Vascular access events will be tracked for both study endpoints and for safety. All vascular access procedures, including both inpatient and outpatient procedures, will be tracked on a monthly basis using a modification of the HEMO Study form 6. Vascular access procedures will include angioplasty, stenting, use of thrombolytics in fistulas or gortex grafts, removal of a permanent access (and reason for removal) and placement of a new permanent access.

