a) Vascular Access Complications: Access infection, stenosis, thrombosis, and intervention will be defined, and a detailed protocol developed to monitor and treat these complications in both groups. The primary measure of vascular access complications will be primary unassisted patency rate (time to first access intervention). Groups will also be compared with respect to: number of access interventions per patient years, time to first thrombosis related access failure, and number of thrombosis related access failures per patient years,

number of access infections per patient years, number of infection related access failures per patient years, time to first infection related access failure.

- b) Iron Losses: Patients on daily hemodialysis have been shown to have increased iron losses compared with conventional patients. Iron utilization will be documented in both groups.
- c) Malnutrition: Although it is anticipated that nutritional status will improve with nocturnal hemodialysis, the potential for malnutrition exists. There may be increased dialytic losses of amino acids due to increased clearances provided with nocturnal hemodialysis. Thus, nutritional status, as outlined in Sections 5.1.3.3 and 5.1.5.3, will be monitored on a regular basis.
- d) Patient Burn-Out: Patient fatigue is a potential concern with the increased frequency of treatments with nocturnal hemodialysis, especially with the requirement that the patients perform the dialysis treatments themselves. The proportion of patients who require a change in dialysis modality lasting more than 2 weeks (back to conventional hemodialysis or to peritoneal dialysis) will be assessed along with reasons for modality change.
- e) Calcium and phosphorus balance: Nocturnal hemodialysis is known to decrease serum phosphate and even lead to hypophosphatemia. Persistently low serum phosphate may lead to weakness, osteomalacia and severe hypophosphatemia (defined as a serum level < 1.0 mg/dl) may cause hemolysis, acute respiratory failure, myocardial depression, or seizures. In addition, nocturnal hemodialysis can lead to negative calcium balance due to calcium loss through ultrafiltration. This may lead to increase of PTH and alkaline phosphatase. These laboratory parameters will be monitored on a regular basis as outlined in Section 3.4.1.d.

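### The planned access-infection rate in Section 5.3(a) cannot be formed as described, because Section 6.3.4 does not record infections that leave the access in place

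*Protocol*

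**What the plan says.** The safety objective in Section 2.1 is to establish the safety of nocturnal hemodialysis "with a particular emphasis on vascular access and patient burden".

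Section 5.3(a) turns this into a monitoring plan: "Access infection, stenosis, thrombosis, and intervention will be defined, and a detailed protocol developed to monitor and treat these complications in both groups". It names one leading measure: "The primary measure of vascular access complications will be primary unassisted patency rate (time to first access intervention"). Among the further group comparisons it lists "number of access infections per patient years, number of infection related access failures per patient years, time to first infection related access failure".

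Section 6.3.4 sets what the vascular access complication form captures. The form is triggered by access failure (thrombosis, or removal that requires a new access), by placement of a new access, or by an access intervention. The section then adds: "Vascular access infections not requiring removal of the access will not be recorded". The form's data go to the DSMB so that it can follow access complication rates by arm.

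Table 8 has five entries under vascular access complications. The only one on infection is "Rate of infection related failures".

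Section 5.2 requires that every adverse event be entered on Form 307, and serious ones on Form 308 as well. Section 6.3.2 has each hospitalization classed as access or non-access.

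**The concern.** Section 5.3(a) treats the infection rate and the infection-related failure rate as two different quantities. The difference between them is the infections that are treated while the access is kept, and Section 6.3.4 says those are not recorded. One section plans a comparison and another removes the data that would distinguish it from its neighbour.

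The protocol itself makes access infection a foreseeable question. Section 1.4 names vascular access complications and greater exposure to venipuncture among the possible harms of nocturnal treatment, and Table 4 gives six sessions per week against three. What is at stake is whether the trial can say anything structured about access infections short of access loss. A later analysis plan could not restore a count that the access form never collected.

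**Working it through.** No sample size, power or event figure is involved, and the protocol states no expected infection rate. The check sets the sections side by side.

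1. **Planned quantity (Section 5.3(a)).** Let R be the access infections that require removal in an arm, S those that do not, and T the patient-years. The planned rate is (R + S) / T. The separate infection-related failure rate is approximately R / T.

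2. **Recorded quantity (Section 6.3.4).** Only R is recorded, so the rate that can be formed is R / T. An infection treated with the access kept, and with no qualifying procedure, meets none of the form's triggers.

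3. **Consequence within an arm.** The recorded rate is the fraction R / (R + S) of the planned one, and it largely coincides with the failure rate listed next to it. The protocol gives no value for R, S or the fraction.

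4. **Consequence between arms.** Write p = R / (R + S) for the share requiring removal. The observed rate ratio is the true ratio multiplied by p(nocturnal) / p(conventional). If p is the same in both arms, the ratio is undistorted and only events are lost. If p differs, the ratio is shifted. Treatment is unblinded and removal is a clinical decision, so equal shares cannot be taken for granted. Nothing in the protocol shows that they differ.

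5. **Other places that could hold S.** Under Section 5.2 such an infection fits the definition of an adverse event, so it belongs on Form 307. That instruction and the exclusion in Section 6.3.4 cannot both be followed literally. The fields listed for Form 307 are severity, relationship, duration and whether the event is serious; none identifies the access. Admitted cases would appear under Section 6.3.2, but outpatient cases would not. No section makes either form the source of the access-infection rate.

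6. **Table 8.** Its single infection entry is the failure rate. It agrees with Section 6.3.4 and disagrees with Section 5.3(a).

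7. **Thrombolytics.** Section 5.1.5.6 counts "use of thrombolytics in fistulas or gortex grafts" as an access procedure. Section 6.3.4 leaves TPA instillation out of its interventions without saying for which access type. Section 9.7 ends primary unassisted patency at the first access procedure or thrombosis.

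**The case against.** The strongest reply is that these infections are not lost. Forms 307 and 308 should take them, access hospitalizations are coded and compared between groups (Section 5.1.5.5 and Table 8), and Sections 10.1 and 10.2 send adverse-event tabulations and hospitalizations by arm to the DSMB. This stands in part. A reader might infer that infections sparing the access are invisible to the DSMB, and the documents do not support that: admitted cases, and any entered as adverse events, can reach it in general tabulations. What is missing is a dedicated count that can serve as the planned rate.

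A second reply is that Table 8 matches Section 6.3.4, so the stray item is one entry in a list of further comparisons. That is fair. It means the conflict could also be settled by narrowing Section 5.3(a), and that some detail was openly deferred there. It does not remove the conflict.

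Third, the primary access measure is time to first intervention, which does not depend on recording infections, and no efficacy endpoint is touched. Both statements are correct. The safety objective also names patient burden beside vascular access, so access is not its only emphasis.

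A reader might also infer that the thrombolytic mismatch undermines the primary access measure. Section 9.7 already ends patency at thrombosis, so a thrombosed fistula or graft treated with thrombolytics counts in any case. No material effect is shown.

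**Conclusion.** The inconsistency is real. As written, the access-infection rate planned in Section 5.3(a) would omit infections that do not require removal and would largely duplicate the infection-related failure rate. Sections 5.2, 5.3(a), 6.3.4 and Table 8 need to be reconciled.

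The effect is confined to one safety comparison within a stated safety emphasis. Its size is unknown: any count of missed infections would rest wholly on assumed rates, so none is offered. Bias between arms is possible but not demonstrated; it would require the share of infections ending in removal to differ by arm. The conclusion assumes only that the access form is the intended source of the rate. The protocol names no other.

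**What to change.** Delete the exclusion in Section 6.3.4. Record each treated access infection, in both arms, on the existing access form with a removal yes/no field. Add the all-infection rate to Table 8, and report both rates by arm to the DSMB.

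The cost is a few extra form entries, one working definition of access infection (which Section 5.3(a) already promises), and some effort to ascertain outpatient infections consistently in patients dialyzing at home. The change concerns data capture only and alters no treatment.

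If this is not done, limit the Section 5.3(a) comparison to infection-related access failures and state that infections without removal are not assessed.

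As a minor tidying step, state in Sections 5.1.5.6, 6.3.4 and 9.7 how thrombolytic use counts for each access type.

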## 6.3.5 Withdrawal from Study Protocol

All withdrawals from the study protocol will be tracked and the reason for withdrawal will be ascertained (see Sections 7.3 and 7.4).

### 7. Deviations from Trial Protocol, Action Items and Stop Points

#### 7.1 Nonadherence

All subjects will be strongly encouraged throughout the study to adhere to the randomized therapy. Deviations from the 3 times per week therapy designated for the conventional home HD arm or the 6 times per week therapy in the nocturnal home hemodialysis treatment arm may occur during the course of the trial, however. Protocols will be developed to treat such deviations in a standardized fashion, with the goal of minimizing the duration and extent of deviations from the planned interventions. Patients will continue to be followed for all data collection, irrespective of their adherence to the randomized therapy (intent to treat analysis).

## 7.2 Action Items

The DCC will report and the Outcome Committee will review (in conjunction with Kinetic Modeling Committee) any patient who has persistent underdialysis (i.e., for conventional home hemodialysis group, not meeting eKt/V of 1.10 per session for 2 or 3 consecutive measurements; for the nocturnal home hemodialysis group, not meeting a std Kt/V of 4.0 for 3 consecutive measurements)

- a) DCC will report and the Recruitment and Adherence Committee will review any patient who has persistent nonadherence to therapy. Persistent nonadherence to be defined and monitored with appropriate action by adherence committee (in conjunction with Kinetic Modeling Committee).
- b) DCC will report and the Standards of Care/Clinical Management Committee will review any patient who has persistent hypophosphatemia (serum phosphate level less than the lower limit of the normal range) on 2 or 3 consecutive monthly measurements
- c) The Central HRQL Survey Center will report within 24 hours to the research coordinator or treating nephrologist any patient who has potentially life-threatening findings on questionnaires done exclusively for the purpose of the study. These findings will also be reported to the DCC who will report these findings in a timely manner to the study center when received by the database. These findings may include, but are not limited to:
  - i) scores above a certain threshold that indicates depression on the Beck Depression Inventory
  - ii) answers 2 or 3 on question #9 of the Beck Depression Inventory ("would you kill yourself")
- d) The Central Cardiac MRI Core will simultaneously transmit a report to the Clinical Center, Data Coordinating Center and Consortium Core for any patient who has potentially clinically relevant findings on tests done exclusively for the purpose of the study. The DCC will report these findings in a timely manner (approximately 2-3 weeks from MRI Core Physician review) to the study center when received by the database. These findings usually include clinically relevant abnormalities noted during the performance of the cardiac MRI. These will relate to abnormalities noted in the pericardium, myocardium, valvular structures and/or contiguous vascular structures. Clinically relevant abnormalities will be adjudicated based on the best clinical judgment of the reviewing physician at the Central Cardiac MRI Core.

## 7.3 Stop Points

It is recognized that certain situations may require premature discontinuation of the randomized therapy (stop-points). Provided the subject does not withdraw consent, data collection and follow-up will continue for all subjects meeting any of the following stop-points in order to perform the intent to treat analysis. Wherever possible and clinically appropriate, efforts should be made by the treating physician and principal investigator to get the patient back into their randomized group. All discontinuations of therapy will be reviewed by the Standards of Care/Clinical Management Committee. Subjects may discontinue the randomized therapy for the following reasons:

- a) The treating physician determines that the subject requires more frequent or less frequent dialysis for reasons including, but not limited to, the following: uremic symptoms, uncontrolled hypertension, patient fatigue/burnout, etc.
- b) **Home hemodialysis patient requests discontinuation of home hemodialysis** for any reason (e.g., burnout/fatigue, home social situation no longer allows, etc.) and refuses to follow the above "non-adherence protocol" described in Section 7.1. The reason for discontinuation of therapy will be documented and the patient will be switched to an alternative dialytic modality.
- c) Home hemodialysis patient unable to perform the HD treatment safely for any reason (as determined by treating nephrologist or principal investigator of the Clinical Center or Safety Committee). The reason for discontinuation of therapy will be documented. Whenever possible, the practicing physician, in conjunction with the Clinical Center physician, should reassess the patient periodically to determine if the patient can go back to nocturnal HD after retraining.

#### 7.4 Losses to Follow-up

Efforts will be made to follow all randomized subjects for 12 months, irrespective of their adherence to the randomized therapy. However, certain situations may preclude complete data collection for the full 12 months (losses to follow-up).

The randomized therapy and routine data collection will be discontinued in the following situations:

- a. Subject withdraws consent for data collection
- b. Subject changes to peritoneal dialysis
- c. Subject receives renal transplant
- d. Subject relocates to a non-study center.

For patients who are lost to routine data collection for reasons b - d above, all attempts will be made to collect vital status. For patients who relocate to a non-study dialysis unit or transfer during their 12 months of follow-up, all attempts will be made to collect vital status, the two co-primary outcomes, and the centrally administered quality of life questionnaires.

All losses to follow-up with reason will be reported to the DCC (discontinuation of therapy form). The Adherence Committee will review all losses to follow-up on a monthly basis.

## 8. Economic Evaluation

### 8.1 Hypothesis

We hypothesize that savings in non-dialysis health care costs due to better health from nocturnal home hemodialysis will offset its additional dialysis related expenses. That is, we hypothesize that nocturnal home hemodialysis will be a "Dominant Strategy" (better outcomes with reduced costs).

### 8.2 Purpose

If nocturnal home hemodialysis proves to be effective in improving health outcomes, it will be important to understand:

- a) The changes in dialysis center costs to provide this mode of hemodialysis,
- b) The changes in overall health care costs to insurers (principally CMS) of patients using this mode of hemodialysis,
- c) The cost-effectiveness of the intervention (change in insurer costs per change in quality adjusted life-years)
- d) Costs per month for in-center hemodialysis (three times per week) obtained from the Daily Trial will be used to compare the monthly costs of nocturnal home hemodialysis with 3 times per week in-center hemodialysis.

The purpose of the economic analysis in this trial is to provide answers to these questions.

### 8.3 Data Collection and Methods

Resource use for patients assigned to either arm of this study will be assessed under the various headings, and by the methods listed in the tables below. Additionally, the following data will be available for economic and other analyses:

- Baseline income and employment status
- Follow up income and employment status
- Baseline vascular access
- All follow up vascular access replacement, repair or removal
- Home modification costs for nocturnal study patients

*General.* To obtain estimates of cost independent of year and geographical differences, we will denominate the use of resources initially in terms of more basic units: hours of nursing or other professional time, outlier adjusted DRG weights for hospitalizations and Medicare allowable charges for other types of payments, specific classes of equipment needed for dialysis and actual supplies used, actual non-injectable drug prescriptions. These will then be given dollar values using consistent references such as published salary scales, national average payments for diagnosis related groups (DRGs) for hospital services and relative value units (RVUs) for professional services, General Services Administration (GSA) contract prices, Red Book average wholesale prescription prices or Average Sales Price (ASP).

Resource use for patients assigned to either arm of this study will be assessed under the various headings, and by the methods listed in the Tables 10 - 13 below.

Cost element	Method of assessment	Calculation of standard cost
Training		
Nursing/technician time for training.	Expert judgment and personnel records of the directors of the home training centers.	Published salary scales for hands-on time/% hands-on time. Range of % hands-on time used for sensitivity assessment.
Professional time by other professional personnel: dietitians, social workers, etc.	Record of visits and times spent at same subset of dialysis sessions.	Published salary scales.
Equipment at each dialysis station	Generic list compiled by consensus of dialysis administrators.	GSA price list, with amortization period determined by consensus. Cost per dialysis will be computed.
Consumable supplies per dialysis	List will be assembled by Cost Subcommittee.	GSA price list.
Routine laboratory tests included in "bundle."	Published charges by large reference laboratories.	Inflation adjusted average published permitted charge.
Overhead	Average overhead from CMS cost reports.	Applied as a percent to total of above.
Home dialysis itself		
Nursing technician time for clinic visits and troubleshooting	Expert judgment and personnel records of the directors of the home training centers.	Published salary scales for hands-on time/% hands-on time. Range of % hands-on time used for sensitivity assessment.
Professional time by other professional personnel: dietitians, social workers, etc.	Record of visits and times spent at same subset of dialysis sessions.	Published salary scales.
Equipment at each dialysis station	Generic list compiled by consensus of dialysis administrators.	GSA price list, with amortization period determined by consensus. Cost per dialysis will be computed.

Table 10:	Center Costs per	Dialysis of Home	Hemodialysis (3 or	6 Times Weekly):
	- · · · · · · · · · · · · · · · · · · ·			

Consumable supplies per dialysis	List will be assembled by Cost Subcommittee.	GSA price list.
Routine laboratory tests included in "bundle."	Published charges by large reference laboratories.	Inflation adjusted average published permitted charge.
Overhead	Average overhead from CMS cost reports.	Applied as a percent to total of above.

Table 11: Patient Costs per Dialysis of Home Hemodialysis (3 or 6 Times Weekly	Table 11: Patient	Costs per Dialy	vsis of Home Hemo	odialysis (3 or 6	Times Weekly)
--	-------------------	-----------------	-------------------	-------------------	---------------

Cost element	Method of assessment	Calculation of standard cost
Home modifications	Data from form 101 and form 260	Accrue to training costs, otherwise TBD.
Unreimbursed costs (phone line, estimated costs of electricity and water, etc.	Periodic costs data	Accrue to maintenance costs, otherwise TBD.

Cost element	Method of assessment	Calculation of standard cost
Injectable medicines given in dialysis units or at home for nocturnal hemodialysis patients.	Data from Forms 203 and 204 collected at baseline, F4, F8 and F12.	Medicare allowable charges for the various agents and doses.
Hospitalizations (Part A)	Estimated from claims for Medicare primary patients in study cohort. Record of ICD9 Diagnostic and Procedure Codes (or Canadian equivalent) and length of stay for all hospitalizations for patients in Medicare HMOs and Canada.	Consistent assignment of DRGs for each hospitalization (with duration adjustment), using "DRG grouper" and related standardized CMS payments.
Hospitalizations (Part B)	Estimated from claims for Medicare Primary patients in study cohort. Total Part B allowed charges corresponding to known dates of hospitalization.	Attribute charges for Medicare Primary to non-Medicare Primary patients with the same DRGs. Standard CMS payments per RVU.
Outpatient medications (Part D)	Data from Form 205 completed at baseline, F4, F8 and F12. Can be crosschecked with data from pharmacy records maintained for Part D expenditures in Medicare patients.	Assign set cost for each medication based on average wholesale price or average sales price.
Non-hospital Medicare covered services	Estimated from claims for Medicare primary payer patients. Data from forms 208 and 209 collected at baseline, F4, F8 and F12. Can be crosschecked with claims data from CMS.	Assignment of CMS HCPCS codes. Standard CMS payments.

 Table 13: Other CMS Covered Medical Care (1):

Comments: (1) In principle, it would be possible to obtain non-dialysis Medicare charges directly from the CMS billing data. However, participants in this trial may be Canadian, members of an HMO (in California), or within the first three years of ESRD on other than Medicare Primary insurance coverage. Therefore we draw inferences from hospital stay data collected within the trial itself. These data include major diagnostic group for the stay, which is used in Medicare pricing. We shall check validity of estimation process by comparing estimates with the actual billed charges in the subset of patients that is Medicare Primary.

Cost element	Method of assessment	Calculation of standard cost
Non-injectable medicines (not covered by Medicare Part D)	Data from Form 205 completed at baseline, F4, F8 and F12 and crosschecked with Part D data.	Prices calculated from "Red Book."
Patient employability or other socially productive activities	Data from Form 105 (at baseline) and Form 233 (at F12).	"Social functional status" recorded and compared.

 Table 13: Other Health Care Related Expenses Not Covered by Medicare

